## 6.2 DSF Dose Modifications

During radiotherapy, if a patient experiences any adverse event that requires dose reduction in the opinion of the investigator and that is considered by the investigator to be possibly, probably, or definitely related to DSF, DSF/Cu should be discontinued and the event will be considered a DLT. If RT has to be temporarily interrupted for technical or medical reasons unrelated to TMZ or DSF/Cu, then treatment with daily TMZ and DSF/Cu should continue. If RT has to be permanently discontinued then TMZ and DSF/Cu should stop until re-initiated at the adjuvant phase of treatment. If TMZ is held due to toxicity unrelated to DSF/Cu, DSF/Cu should continue as tolerated.

During adjuvant TMZ, the dose of DSF may be reduced from 500 mg per day to 250 mg per day due to toxicity or intolerance at the discretion of the treating physician. Expansion patients who discontinued DSF during RT and concurrent TMZ due to toxicity may be considered to resume DSF with adjuvant TMZ but at 250 mg/day as long as the toxicity has resolved prior to the start of cycle 1 of adjuvant TMZ and after discussion between the treating physician and the PI. Special attention should be paid to neurological symptoms such as delirium/psychosis, gait disturbance/ataxia, and peripheral neuropathy. A grade 2 toxicity of the above neurological symptoms should prompt a consideration for further work-up and consideration of dose reduction if thought to be related to DSF. No second dose reduction (below 250 mg/day) is allowed—if a second dose reduction is required, DSF and Cu will be permanently discontinued. Of note, hematologic toxicity is uncommon for DSF and is likely related to TMZ.

### **6.2.1 Administration of DSF to Patients with Abnormal Hepatic Function**

DSF/Cu should only be administered if hepatic function is within the parameters established in the eligibility criteria. Hepatic toxicity from DSF/Cu is uncommon but may occur. Therefore, hepatic dysfunction that occurs while the patient is on study should prompt an evaluation to determine the cause, including the possibility of hepatotoxicity from concurrent medications including TMZ.

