As for the rationale for the proposed expansion cohort, this is based on the promising finding of the dose-escalation phase of the study. After enrollment of the 18 patients for the dose-escalation phase, 8 patients were treated with DSF of 250 mg/day (dose level 2) and 10 patients with 375 mg/day (dose level 3). Three dose-limiting toxicities (DLTs) were observed: 1 with 250 mg/day (grade 2 urinary incontinence and ataxia), and 2 with 375 mg/day (both grade 3 elevated liver enzymes). The TITE-CRM model estimated the DLT probability of DSF to be 10% (95% CI: 3-29%) at 250 mg/day, and 21% (95% CI: 7-42%) at 375 mg/day. Thus, we have declared that the MTD of DSF in combination with RT/TMZ/Cu for GBM is 375 mg/day, and the recommended phase II dose is 250 mg/day. Furthermore, tumor mutations were evaluated with next-generation sequencing for all patients to explore possible biomarkers for response. Notably, GBM patients with *IDH* (n = 6), *BRAF* (n = 2), and *NF1* (n = 1) mutations exhibited much better PFS and OS than those without these mutations (n = 9): 1-year PFS of 100% vs 22%, respectively, p = 0.001; 1-year OS of 100% vs 42%, respectively, p = 0.006. Given that the historical PFS and OS of newly diagnosed GBM patients treated with RT and TMZ is approximately 27% and 60% at one year [4], respectively, the preliminary data of this molecular subset of GBM are thought-provoking and raise the possibility that these mutations make GBM tumors more sensitive to DSF/Cu in combination with chemoradiotherapy. Interestingly, all three mutations, which affect approximately 15-20% of GBM tumors, make tumor cells more dependent on glutamate for cellular metabolism [68-70]. As DSF metabolite can affect glutamate uptake, this may be the biological mechanism for the improved outcomes for GBM with these mutations. Thus, we have proposed to add an expansion cohort to this phase I/II study to treat additional GBM patients with *IDH*, *BRAF*, or *NF1* mutations to increase the statistical power of our preliminary finding.

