The Time-to-Event Continual Reassessment Method (TITE-CRM) proposed by Cheung and Chappell is an adaptive Phase I design [80]. In a TITE-CRM clinical trial, patients enroll as they become available to be studied. Each participant is assigned to a dose level from a set of dose levels pre-defined by investigators and is monitored for DLTs over time. The design is adaptive in that the dose level assigned to a newly enrolled patient depends on the dose level assignments and DLT outcomes of the patients already in the study. A patient's observation period ends at the occurrence of a DLT, or if a DLT does not occur, after a fixed time T of follow-up. The trial ends when a fixed number of patients,  $n$ , have been observed. Once the final patient has been observed, the MTD can be estimated using the available data. The TITE-CRM differs from the traditional CRM in that the estimation process is weighted to account for the proportion of the observation period that each currently enrolled patient has been observed. By not requiring complete observation before the enrollment of the next patient, new participants can be assigned a dose and begin evaluation as they become available, subsequently shortening the overall duration of the study.

The Biostatistics Unit at the University of Michigan Comprehensive Cancer Center has developed a program `titecrm.sas` for SAS 9 (SAS Institute, Inc.; Cary, NC) that makes all of the calculations necessary to determine dose allocation of a trial in real-time. They have also developed simulation programs that allow the user to determine the efficacy of the trial based on *a priori* estimates of the probabilities of toxicity and necessary sample sizes.

In order to properly utilize this type of trial, a few assumptions and many rules must be determined before the start of the trial. The main assumption that must be determined is how many different dose levels will be included in the trial and *a priori* estimates of the probability of a DLT at each of those dose levels. For this trial, we have 4 dose levels ( $d_1, \dots, d_4$ ) ranging from 125mg PO daily to 500 mg PO daily, with initial toxicity probability estimates ( $p_1, \dots, p_4$ ) ranging from 0.05 to 0.30, respectively. The following table shows the dose design with associated estimated probabilities of toxicity.

Dose Escalation Schedule		
Dose Level	Dose of DSF	Initial Toxicity Estimate
Level 1	125 mg PO daily	0.05
Level 2	250 mg PO daily	0.10

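### Sections 6.2 and 6.2.1 give unreconciled stop/continue instructions for DSF/Cu when liver tests exceed the eligibility limits, and the DLT attribution wording leaves a narrower gap

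*Combined protocol and SAP*

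**What the plan says.** All references are to the combined protocol and SAP.

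- **Section 3.1** sets the entry limits: AST and ALT below 3 x ULN, total bilirubin at most 2 x ULN.
- **Section 6.2.1**, under Dose Modifications and titled for patients with abnormal hepatic function, says "DSF/Cu should only be administered if hepatic function is within the parameters established in the eligibility criteria". No attribution condition is attached. Its last sentence says that "hepatic dysfunction that occurs while the patient is on study should prompt an evaluation to determine the cause", with no instruction to hold, resume or stop.
- **Section 6.2, during RT**: if the investigator thinks a dose reduction is required and considers the event "possibly, probably, or definitely related to DSF, DSF/Cu should be discontinued and the event will be considered a DLT". The same paragraph says that when TMZ is held for toxicity not related to DSF/Cu, DSF/Cu carries on so long as it is tolerated.
- **Section 6.2, adjuvant phase**: "the dose of DSF may be reduced from 500 mg per day to 250 mg per day due to toxicity or intolerance at the discretion". The decision rests with the physician who treats the patient, and no liver limit is named.
- **Section 6.1** holds concurrent TMZ for a grade 3 non-hematologic event, with listed exceptions that do not include liver enzymes. It also lets the physician hold TMZ at discretion.
- **Section 5.9.2** makes bilirubin above 2.0 x ULN, or AST or ALT above 3.0 x ULN, a DLT. That bullet has no wording on relation to DSF, but the opening sentence of the section excludes events attributed to TMZ, concomitant medication, progression, intercurrent illness or adjuvant DSF.
- **Sections 2.0 and 14.1** count a toxicity as a DLT if it is at least possibly related to DSF/Cu.
- **Section 1.3** reports the escalation result: "8 patients were treated with DSF of 250 mg/day (dose level 2) and 10 patients with 375 mg/day (dose level 3"), with three DLTs, of which "2 with 375 mg/day (both grade 3 elevated liver enzymes").

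**The concern.** Section 6.2.1 reads as a limit on giving the drug, whatever the cause of the abnormality. Section 6.2 makes stopping depend on the investigator's view of cause and of the need to reduce, and in one situation tells the site to keep going. A site that reads one section will treat the same patient differently from a site that reads the other.

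The rule will be consulted repeatedly. LFTs are scheduled monthly during RT and at each adjuvant cycle (Sections 5.5 and 10.2). Liver enzymes produced most of the DLTs seen so far, and DSF is planned at 500 mg/day with adjuvant TMZ for up to six 28-day cycles (6 x 28 days = 24 weeks).

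The consequences are uneven exposure to DSF/Cu above the liver limits, discontinuation counts that depend on the passage followed, and DLT counts that may not be comparable. DLTs are still reported: Section 7.4 keeps the 18-week DLT window, and Section 13.0 requires the number of DLTs in the semi-annual safety report.

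**Working it through.** **1. The plan's own figure.** Section 1.3 gives DLT probabilities of "10% (95% CI: 3-29%) at 250 mg/day, and 21% (95% CI: 7-42%) at 375 mg/day". Inputs: initial estimates 0.05, 0.10, 0.20, 0.30 (Section 14.3.1, "ranging from 0.05 to 0.30, respectively"); 1 DLT in 8 patients at 250 mg/day and 2 in 10 at 375 mg/day. The documents state neither model form nor prior, so I assumed a one-parameter power model, p^theta, with an exponential(1) prior and full follow-up. Plugging in the posterior mean of theta gives 10.5% (95% credible interval 2.4-30.0%) and 20.7% (7.4-43.1%). A normal prior or a logistic model gives 10.5-11.4% and 20.7-22.0%. The stated figures are reproduced with both liver events counted as DLTs.

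**2. Do the numerical limits agree?** Bilirubin: at most 2 x ULN (3.1) against above 2.0 x ULN (5.9.2), exactly complementary. AST/ALT: below 3 x ULN against above 3.0 x ULN, differing only at exactly 3.0. So the conflict is about action and attribution, not thresholds.

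**3. Stop or continue.** Take a liver test above the 3.1 limits and read 6.2.1 as applying at each administration:

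| Situation | 6.2.1 | 6.2 |
|---|---|---|
| RT; judged DSF-related; investigator wants a reduction | not given | discontinue, DLT |
| RT; judged DSF-related; no reduction thought necessary | not given | no stop directed |
| RT; grade 3 rise attributed to TMZ, TMZ held under 6.1 | not given | continue if tolerated |
| RT; attributed to another drug, TMZ not held | not given | silent |
| Adjuvant phase | not given | 250 mg/day permitted at discretion |

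The sections agree in the first row. The third row is a direct conflict: one instruction withholds DSF/Cu and the other continues it. TMZ is a cause that 6.2.1 itself names as a possibility. The fifth row conflicts unless the discretion in 6.2 is silently subject to 6.2.1. The documents do not reproduce the CTCAE grade boundaries, so the third row is conditioned on a rise that is both grade 3 and above the 3.1 limits.

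**4. DLT status.** Take an AST or ALT above 3.0 x ULN, possibly due to DSF and possibly due to TMZ, with dosing unchanged.

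- Under 2.0 and 14.1 it counts, because a possible relation to DSF/Cu suffices.
- Under the opening sentence of 5.9.2 it may not count, because events attributed to TMZ are excluded.
- If it passes that sentence, the laboratory bullet makes it a DLT, although the DLT clause in 6.2 is not triggered because no reduction was judged necessary.

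The last item is not a strict contradiction, since 6.2 does not claim to list every DLT. A site working from 6.2 alone could still miss the event.

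**5. How many patients.** Liver DLTs: 2 of 3 DLTs, and 2/18 = 11.1% of patients. The expansion needs 24 - 9 = 15 more patients (14.3.5). 15 x 2/18 = 1.7. The exact 95% interval for 2/18 is 1.4-34.7%, and multiplying by 15 gives 0.2 to 5.2 patients. By dose, 2/10 were at 375 mg/day and 0/8 at 250 mg/day (exact 95% interval 0-37%). Expansion patients receive 250 mg/day during RT, so the pooled rate is an extrapolation. It also leaves out liver rises that were not DLTs, such as those attributed to TMZ.

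**The case against.** The best reply is that 6.2 is a general rule that never mentions liver enzymes and 6.2.1 is its liver-specific subsection, so the specific text governs and the adjuvant discretion operates inside the liver limits. Alternatively, 6.2.1 can be read as an entry condition only. Either reading would remove the conflict. Neither is stated, and they give opposite answers for a patient on treatment. The title of 6.2.1, its place among dose modifications and its reference to dysfunction on study count against the entry-only reading, while its closing request for evaluation alone counts against a firm bar.

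Several stronger readings are tempting and are not supported:

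- **That 6.2, 6.2.1 and 5.9.2 hold three competing stop and DLT rules.** 5.9.2 has no stop rule, 6.2.1 has no DLT rule, and the DLT clause of 6.2 repeats a bullet of 5.9.2.
- **That one patient could be stopped, reduced or continued at the same moment.** 6.2 offers no reduction step during RT; reduction exists only in the adjuvant phase.
- **That a rise due to another drug has unclear DLT status.** The opening sentence of 5.9.2, with 2.0 and 14.1, settles it as not a DLT.
- **That the MTD or RP2D is in doubt.** Escalation is complete and both liver events were counted. Leaving one out would lower the 375 mg/day estimate from 20.7% to 15.2% (14.2-16.3% across the models tried), but nothing in the documents suggests that either was misclassified.
- **That the OS analysis set is materially affected.** Evaluability needs at least 4 weeks of DSF with RT (14.3.5). With LFTs monthly during RT unless clinically indicated sooner, scheduled testing would seldom force a stop before then.
- **That liver toxicity will dominate the adjuvant phase.** The table of the sponsor's previous study at 500-1000 mg/day (Section 1.2.6) lists no hepatic event of grade 2-3 related to DSF, and Section 1.2.10 describes the related toxicities as neurological. Nor will every patient reach 500 mg/day: adjuvant TMZ is optional, progression ends DSF, and expansion patients who stopped for toxicity may resume only at 250 mg/day.

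**Conclusion.** The point holds as a contradiction in dosing instructions with a secondary gap in DLT attribution. For a liver test above the Section 3.1 limits, 6.2.1 withholds DSF/Cu regardless of cause. Section 6.2 continues it in the TMZ-attributed case and permits a reduced dose in the adjuvant phase. The gap in DLT status is confined to enzyme rises possibly due to both DSF and TMZ, and to those above 3.0 x ULN that lead to no dosing change.

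The number affected is small and uncertain: about 1.7 of 15 further patients (0.2 to 5.2) if the pooled escalation rate carried over, with no liver DLT in 8 patients at the expansion dose used during RT. This rests on reading 6.2.1 as applying on treatment, which the text suggests but does not say. What is affected is consistent dosing, patient safety and safety reporting. The declared MTD and RP2D stand, and any effect on the OS endpoint is minor. The case for acting rests on the safety relevance of the rule and the low cost of the change, not on the event count.

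**What to change.** 1. Reconcile Sections 6.2 and 6.2.1 in one liver statement, set out separately for RT and for the adjuvant phase. It should say whether the 3.1 limits apply at each administration or only at entry, and whether attribution to DSF/Cu, TMZ or another cause governs stopping. It should also say how it relates to the sentence on continuing DSF/Cu while TMZ is held and to the discretionary adjuvant reduction.
2. Align the attribution wording of the liver bullet in 5.9.2 with 2.0, 14.1 and 6.2. State how a rise possibly due to both DSF and TMZ is classed, and whether the laboratory threshold alone makes a DLT when dosing is unchanged.
3. Cross-refer to that statement from the other sections.

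Which clinical rule holds is for the investigators to decide; none is proposed here. The cost is wording in a protocol amendment. No tests are added, because LFTs are already scheduled in both phases.

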### **6.2.2 Hypersensitivity Reactions**

Hypersensitivity reactions rarely occur. If they do occur, minor symptoms such as flushing, skin reactions, dyspnea, lower back pain, hypotension, or tachycardia may require no intervention; however, severe reactions, such as hypotension requiring treatment, dyspnea requiring bronchodilators, angioedema, or generalized urticaria require immediate discontinuation of study drug administration and aggressive symptomatic therapy. Patients who experience a severe hypersensitivity reaction to DSF should discontinue DSF immediately and should not be re-challenged.

## **7.0 REGULATORY AND REPORTING REQUIREMENTS**

The entities providing oversight of safety and compliance with the protocol require reporting as outlined below.

The Washington University Human Research Protection Office (HRPO) requires that all events meeting the definition of unanticipated problem or serious noncompliance be reported as outlined in Section 7.2.

### **7.1 Definitions**

#### **7.1.1 Adverse Events (AEs)**

**Definition:** any unfavorable medical occurrence in a human subject including any abnormal sign, symptom, or disease.

**Grading:** the descriptions and grading scales found in the revised NCI Common Terminology Criteria for Adverse Events (CTCAE) version 4.0 will be utilized for all toxicity reporting. A copy of the CTCAE version 4.0 can be downloaded from the CTEP website.

**Attribution (relatedness), Expectedness, and Seriousness:** the definitions for the terms listed that should be used are those provided by the Department of Health and Human Services' Office for Human Research Protections (OHRP). A copy of this guidance can be found on OHRP's website:

<http://www.hhs.gov/ohrp/policy/advevntguid.html>

### **7.1.2 Serious Adverse Event (SAE)**

**Definition:** any adverse drug experience occurring at any dose that results in any of the following outcomes:

- Death
- A life-threatening adverse drug experience
- Inpatient hospitalization or prolongation of existing hospitalization
- A persistent or significant disability/incapacity (i.e., a substantial disruption of a person's ability to conduct normal life functions)
- A congenital anomaly/birth defect
- Any other experience which, based upon appropriate medical judgment, may jeopardize the subject and may require medical or surgical intervention to prevent one of the outcomes listed above

### **7.1.3 Unexpected Adverse Experience**

**Definition:** any adverse drug experience, the specificity or severity of which is not consistent with the current investigator brochure (or risk information, if an IB is not required or available).

### **7.1.4 Life-Threatening Adverse Experience**

**Definition:** any adverse drug experience that places the subject (in the view of the investigator) at immediate risk of death from the reaction as it occurred, i.e., it does not include a reaction that, had it occurred in a more severe form, might have caused death.

### **7.1.5 Unanticipated Problems**

**Definition:**

- unexpected (in terms of nature, severity, or frequency) given (a) the research

procedures that are described in the protocol-related documents, such as the IRB-approved research protocol and informed consent document; and (b) the characteristics of the subject population being studied;

- related or possibly related to participation in the research (in this guidance document, possibly related means there is a reasonable possibility that the incident, experience, or outcome may have been caused by the procedures involved in the research); and
- suggests that the research places subjects or others at a greater risk of harm (including physical, psychological, economic, or social harm) than was previously known or recognized.

#### **7.1.6 Noncompliance**

**Definition:** failure to follow any applicable regulation or institutional policies that govern human subjects research or failure to follow the determinations of the IRB. Noncompliance may occur due to lack of knowledge or due to deliberate choice to ignore regulations, institutional policies, or determinations of the IRB.

#### **7.1.7 Serious Noncompliance**

**Definition:** noncompliance that materially increases risks, that results in substantial harm to subjects or others, or that materially compromises the rights or welfare of participants.

#### **7.1.8 Protocol Exceptions**

**Definition:** A planned deviation from the approved protocol that are under the research team's control. Exceptions apply only to a single participant or a singular situation.

Pre-approval of all protocol exceptions must be obtained prior to the event.

### **7.2 Reporting to the Human Research Protection Office (HRPO) at Washington University**

The PI is required to promptly notify the IRB of the following events:

- Any unanticipated problems involving risks to participants or others which occur at WU, any BJH or SLCH institution, or that impacts participants or the conduct of the study.
- Noncompliance with federal regulations or the requirements or determinations of the IRB.
- Receipt of new information that may impact the willingness of participants to participate or continue participation in the research study.

These events must be reported to the IRB within **10 working days** of the occurrence of the event or notification to the PI of the event. The death of a research participant that qualifies as a reportable event should be reported within **1 working day** of the occurrence of the event or notification to the PI of the event.

### **7.3 Reporting to the Quality Assurance and Safety Monitoring Committee (QASMC) at Washington University**

The PI is required to notify the QASMC of any unanticipated problem occurring at WU or any BJH or SLCH institution that has been reported to and acknowledged by HRPO as reportable. (Unanticipated problems reported to HRPO and withdrawn during the review process need not be reported to QASMC.)

QASMC must be notified within **10 days** of receipt of IRB acknowledgment via email to a QASMC auditor.

### **7.4 Timeframe for Reporting Required Events**

Adverse events will be tracked until the last dose of DSF. However, DLTs will only be evaluated for 18 weeks from the first day of DSF with RT+TMZ or at least 12 weeks following the completion of RT in the event there is a delay/interruption of RT. All clinically or laboratory adverse events that are > grade 1 (excluding lymphopenia) will be collected.

## **8.0 PHARMACEUTICAL INFORMATION**

### **8.1 Disulfiram**

#### **8.1.1 DSF Description**

DSF is an alcohol antagonist drug approved by the FDA for the treatment of alcoholism. Its powder is white, odorless, and almost tasteless. It is soluble in water to the extent of about 20mg in 100mL, and in alcohol to the extent of about 3.8 g in 100 mL.

**Molecular formula:** C10H20N2S4

**Chemical name:** bis(diethylthiocarbamoyl) disulfide.

**Molecular weight:** 296.54.

